#### Secondary hypotheses:

- 1. Comparison of intervention groups with secondary outcomes listed below.
- 2. Primary and secondary hypotheses comparisons will be confirmed in gender specific strata.

**Endpoints:** Primary outcome: Change in BPI total score over the 12-month follow-up period. Secondary outcomes will include measures captured in EHR (e.g., medication prescription/refills, health care visits for pain management), as well as patient-reported measures related to pain, comorbid mental health conditions and function, expected mediators of treatment effects, patient satisfaction, and adverse effects. These outcomes will be assessed at 10 weeks, 6 months and 12 months.

**Randomization.** Participants will be randomized to Mobile+Group MBI, Mobile MBI or Usual Care (UC; 1:1:1) after all eligibility components are completed. (See 5.4 for eligibility component details.) During the phone call the participant will be randomized and will be told whether they have been selected to be in UC or one of the two intervention groups. The randomization list will be concealed from the research team within the tracking application, so team members will not know the next study assignment. Permuted blocks will be used to aid in the concealment of treatment assignment while ensuring balance in treatment arms across time.

**Usual Care Control Condition.** Participants assigned to the Usual Care (UC) condition will be told their group assignment during the randomization phone call described in the Randomization paragraph above. They will also be mailed a letter confirming their assignment.

**Intervention Conditions.** Participants assigned to the Mobile MBI or Mobile+Group MBI intervention groups will be told their group assignment during the randomization phone call

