#### Expected participation in Phase 2 trial

We base proposed estimates on our experience conducting previous successful trials with Veterans with chronic pain (ACTION, SPACE, EPOCH, ECLIPSE). Study participants will be recruited from the Minneapolis, Indianapolis, Greater Los Angeles and Durham VA Health Care Systems, using a process successfully used in prior studies by members of our research team, and piloted during Phase 1 of this project. The four facilities have about 80,000 patients who meet our initial eligibility criteria. We estimate from our Phase 1 pilot a randomization rate of 2.5% but an increased randomization rate when using approach #2, email recruitment. Therefore, we will need to screen approximately 100,000 patients in order to reach our recruitment goal of up to 950 randomized. We want an approximately balanced sample of men and women. We estimate women will respond at up to 3 times the rate of men (approximately 4.5% for women and almost 2% for men). If we screen a large portion of the sample of eligible women (about 20,000) and about 1/3 of the eligible men (about 80,000), then we should reach our recruitment goal of up to 950 randomized, with nearly balanced men and women. Among those randomized, we are conservatively planning that up to 20% might be missing complete follow-up data but based on past work we believe the actual level of missing data will be closer

to 10-15%. Ultimately, this would yield a randomized N= up to 950 and with retention of 600 or greater participants at 6 and 12 months.

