#### Power and Sample Size Estimate

Our power calculation uses the total BPI score as the primary outcome measure. For our primary analysis we estimate there will be 200 participants in each of the three treatment arms with complete data for a total of 600 people with complete data from a total of up to 950 randomized. Two hundred participants in each arm would yield 80% power to reject the null hypothesis of equal means if any of the three arms differed from each other by an effect size of 0.33 or greater. This is based on an alpha level of 0.0167 (Bonferroni correction of 0.05/3 = 0.0167) for each of the three comparisons (Mobile+Group vs Usual Care, Mobile vs Usual Care, and Mobile+Group vs Mobile). Using the same assumptions, there would be 90% power to detect differences of 0.38 or greater. The BPI has been found to have a minimally clinically important difference of approximately 1 point and the standard deviation from prior studies is around 2 points, which is consistent with a minimally important clinical difference in effect size of around 0.5.

As a secondary analysis we will look at a categorical responder analysis, in which we define clinically significant changes as a 30% reduction in BPI score from baseline. This is an accepted threshold for clinically significant improvement in clinical trials and recommended by the IMMPACT guidelines.

Previous studies demonstrate that a 30% reduction on the BPI is a clinically important difference. Prior studies have shown that 15-20% of UC patients demonstrate a 30% reduction in pain function score from baseline to follow-up. With 200 people in each arm there would be 80% power to detect absolute differences of greater than 13.3%, 14.3%, and 16%, respectively, based on assumptions of 15%, 20% or 35% in the comparison arms (accounting Bonferroni corrections for comparisons of Mobile+Group vs Usual Care, Mobile vs Usual Care, and Mobile+Group vs Mobile).

Based on the conservative estimate of 20% attrition, we propose randomizing at least 250 per arm to ensure that we maintain a minimum effective size of 200 per group (250 people per group\*.80=200). If we instead achieve the anticipated attrition rate of only 10% then our sample will be approximately 225 per arm.

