#### General Analytic Approach.

We will use an intention-to-treat approach. Preliminary descriptive analyses will summarize the distributions of the baseline measures across treatment arms overall and by gender and will similarly assess the outcome distributions across assessment time points. We will summarize the completeness of the self-reported outcome assessments and examine associations between completeness and baseline measures as well as the association with secondary outcome assessments that are collected from the electronic medical record (e.g. medications, health care utilization related to pain treatment). In previous studies, we have observed outcome completion rates in excess of 90% at each assessment time-point. Initial analyses will use all

available follow-up data and subsequent sensitivity analyses will examine the potential effect of response bias.

For analyses of the primary outcome, all repeated measurements of the BPI score will be fitted in a mixed model for repeated measures as a function of the group assignment, while controlling for time points and baseline values of the outcome as fixed effects, with participants as random effects. Between-group differences over the entire follow-up period will be tested as the primary test of treatment group differences (this will be done for all three comparisons of the Mobile, Mobile+Group, and Usual Care arms). Between-group differences will be estimated for each of the time points (e.g. 10 weeks, 6 months and 12 months). The secondary outcomes physical function, anxiety, depression, fatigue, sleep disturbance, participation in social roles and activities, patient-ratings of improvement, and PTSD) will be similarly analyzed using the same linear mixed effect models for normal continuous measures and appropriate generalized linear mixed effect models for non-normal measures. For example, the BPI responder analyses will use generalized linear mixed effect models with binomial distributions and either log or logit links, which ever best fit the data, for the repeated dichotomous outcomes of a 30% reduction from baseline in BPI scores over the 12-month study period.

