Additional exploratory analyses involve the assessment of the extent to which amount of mindfulness practice, pain acceptance, pain-related fear avoidance, pain management self-efficacy, mindfulness skills, and perceived stress mediate the effects of the intervention. The indirect effects of these potential mediators will be tested using the bootstrap approach to obtaining confidence intervals to avoid the often-violated assumption underlying Sobel's (1982) method that the sampling distribution of the indirect effect will be normal. Similar to the methods described above for the primary analyses, weighted selection model analyses will examine sensitivity of results to response biases.

To assess the sensitivity of these initial analyses to response bias, we will fit a series of weighted selection model analyses. Each analysis will use an EM algorithm to estimate weights to assign to potential values of the missing outcomes for use in the regression model. Models will be varied to use different combinations of the following variables—intervention, observation and value of the outcome at various assessments, and baseline covariates together with pain measurements and services utilization over the follow-up period—as predictors to consider different potential missing at random and missing not at random mechanisms generating the missing data.

It has been hypothesized that men and women may respond differently to the interventions and this might be particularly true for the group-based portions of the intervention. An interaction between treatment and gender will be assessed, however tests for interaction tend to be underpowered and this is an important area of concern, so gender stratified results will be presented in secondary analyses even if statistical evidence of interaction is not found.

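### The primary mixed model omits gender, a known design variable; adding it as a fixed effect is a small improvement at almost no cost

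*Combined protocol and SAP*

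**What the plan says.** **Allocation.** The Randomization paragraph of section 5.1 sets a 1:1:1 ratio and says: "Permuted blocks will be used to aid in the concealment of treatment assignment while ensuring balance in treatment arms across time". It gives balance over time as the only balance aim and names neither a stratification factor nor a block size.

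**Primary model.** Under General Analytic Approach in section 5.6, the repeated BPI scores are modelled on group, "controlling for time points and baseline values of the outcome as fixed effects, with participants as random effects". Gender and site are not listed.

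**Gender elsewhere in the plan.**
- Expected participation (section 5.6) sets recruitment rates by gender and states: "We want an approximately balanced sample of men and women". Section 5.2 instead expects about 40% women.
- The secondary hypotheses call for the comparisons to be confirmed within each gender.
- Section 5.6 plans a treatment-by-gender test and adds that "gender stratified results will be presented in secondary analyses even if statistical evidence of interaction is not found".
- The Introduction reports more moderate to severe pain among women Veterans than men, and more mental health or substance use diagnoses (46% against 32%).

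**The concern.** Gender is recorded for everyone before randomisation, since demographics are a baseline measure and the baseline survey must be complete first. The plan treats gender as a design factor in recruitment and reporting, yet leaves it out of its main model.

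Two things are at stake. First, any variance in follow-up BPI that gender explains beyond baseline BPI stays in the error term and slightly widens all three primary confidence intervals. Second, up to 20% of participants may lack complete follow-up, and the initial analyses use all available data. The Introduction links the group format to women's discomfort and to drop-out, and only one arm has groups. If gender predicts both missingness and outcome, the missing-at-random assumption is more credible with gender in the model.

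**Working it through.** **Inputs from the plan (Power and Sample Size Estimate).** "Two hundred participants in each arm would yield 80% power to reject the null hypothesis of equal means"; the detectable difference attached to that figure is 0.33 SD, with 0.38 SD for 90% power. On alpha: "This is based on an alpha level of 0.0167 (Bonferroni correction of 0.05/3 = 0.0167) for each of the three comparisons". The SD is about 2 BPI points and the minimally important difference about 1 point. Sidedness is not stated; two-sided is taken because the aim is to "reject the null hypothesis of equal means".

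**Assumed.** The share R2 of residual variance explained by gender beyond arm and baseline BPI is not in the documents. The range used is 1% to 5%.

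**1. Reproduce the stated power.** With residual SD σ = 1, power = Φ(δ / (σ√(2/n)) − z), where z = 2.394 for two-sided alpha 0.05/3 and √(2/200) = 0.1.
- δ = 0.33: Φ(3.30 − 2.394) = 81.8% (81.4% with the noncentral t). Stated: 80%.
- δ = 0.38: Φ(3.80 − 2.394) = 92.0% (91.8% with the t). Stated: 90%.

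The stated figures hold, slightly on the cautious side, and do not depend on gender adjustment.

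**2. Add gender.** Replace σ by √(1 − R2). The equivalent gain in completers is 600/(1 − R2) − 600.

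| R2 | Power at 0.33 | Detectable effect, 80% power | Equivalent extra completers |
|---|---|---|---|
| 0 | 81.8% | 0.324 | 0 |
| 1% | 82.2% | 0.322 | 6 |
| 2% | 82.6% | 0.320 | 12 |
| 5% | 83.9% | 0.315 | 32 |

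**3. How large a gender effect does that need?** With a proportion p of women and a difference of g residual SDs, R2 = q/(1 + q), where q = p(1 − p)g². For g = 0.2, R2 is 0.95% at p = 0.4 and 0.99% at p = 0.5. For 5% at p = 0.4, q = 0.0526, so g = √(0.0526/0.24) = 0.47. Gender alone is therefore more likely to sit near the bottom of the range.

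**4. Chance imbalance.** With 250 per arm, the SD of the between-arm difference in the share of women is √(2p(1 − p)/250): 4.4 points at p = 0.4 and 4.5 at p = 0.5. At p = 0.4 the 95% range is ±1.96 × 4.38 = ±8.6 points. If gender shifts the outcome by 0.2 SD (assumed), that extreme moves a contrast by 0.086 × 0.2 = 0.017 SD, or about 0.03 BPI points.

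**5. Inside the gender strata.** In 4,000 simulated unstratified lists (block size 6 assumed, N = 750, 40% women, about 100 women per arm), the gap between the largest and smallest arm among women has median 12 and 95th percentile 26. The worst pairwise variance rises by 3.3% (median) and 7.8% (95th percentile). At 80 women and 120 men analysed per arm, power at 0.33 is about 38% and 56%, so stratum size is the limit.

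**6. Differential drop-out, illustrated with assumed rates.** Start with 40% women. Suppose Mobile+Group loses 35% of women and 10% of men, and usual care loses 20% of each. Women are then 0.26/(0.26 + 0.54) = 32.5% of Mobile+Group completers and 40% of usual-care completers. At 0.2 SD this 7.5-point gap is worth 0.015 SD. It is small, but it is systematic: stratified allocation would not prevent it, while a gender term addresses it.

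**The case against.** The strongest reply is that nothing here is broken. Chance imbalance is not bias, and the confidence interval already allows for it. Baseline BPI, probably the main prognostic variable, is in the model. The precision gain rests on an assumed R2, and the plan has more headroom elsewhere: 950 randomised with 20% loss leaves 760 completers, about 253 per arm, with power near 90% at 0.33. The plan's statement that men and women may respond differently concerns interaction, which a gender main effect does not address and which section 5.6 already tests separately. All of this stands, and it limits the size of the point.

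A reader might go further and infer that gender and site are both wrongly ignored, that imbalance passes directly into the contrasts, and that blocks should be built within gender by site. The documents do not support that:
- Section 5.1 has all study steps run by staff at one centre, with delivery by app and videoconference. Site is where patients come from, not where treatment is given.
- The plan is silent on stratification; it does not rule it out.
- Eight gender-by-site lists would leave more incomplete blocks and loosen the balance over time that section 5.1 seeks.
- The text is Version 16, dated March 2024, and does not say whether allocation is still open.

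Two cautions about cost also stand. In a logit-link responder model, added covariates change the conditional odds ratio being estimated. A late change to the primary model of an open-label trial carries a credibility cost. Neither weighs against adding gender to the linear models before outcomes are seen by arm.

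**Conclusion.** The point holds as a small improvement, not as an error. The primary contrasts are unbiased under randomisation and keep their stated power as planned. Adding gender would raise power at 0.33 by about 0.4 to 2.1 percentage points (81.8% to 82.2-83.9%), if gender explains 1% to 5% of residual variance. A 0.2 SD gender effect corresponds to the low end. Any protection against gender-related drop-out is a further benefit whose size the documents cannot give, because they contain no follow-up rates by gender. The case for site is weaker, and stratified allocation would not rescue the underpowered gender strata.

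**What to change.** - **Section 5.6, General Analytic Approach:** add gender as a fixed effect to the primary mixed model and to the linear secondary-outcome models, fixed before outcomes are seen by arm. Site may be added as an option.
- **Responder models:** where a logit link is used, state which covariates are included and that the odds ratio is conditional on them.
- **Section 5.1, Randomization:** state whether the concealed list is stratified. If it is, include its factors in the model; leaving them out would make the standard errors too large. If it is not and allocation is still open, generate the blocks within gender, not within eight gender-by-site lists. If allocation has closed, adjustment in the model is the remaining remedy.

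The cost is a line of analysis text, one model degree of freedom for gender (three more if the four sites are added) and a protocol amendment through the Central IRB. No extra patients or data are needed. A new allocation list is needed only if blocks are stratified from now on.

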The group format can also pose a barrier, especially for female Veterans. Between 15-40% of female Veterans using VA services have experienced military sexual trauma (MST) (defined as "physical assault of a sexual nature, battery of a sexual nature, or sexual harassment which occurred while the veteran was serving on active duty or active duty for training"), and a recent survey found that 24% experienced sexual harassment at their VA Healthcare System (VAHCS). Not surprisingly, some female MST patients report discomfort participating in Mindfulness-Based Stress Reduction (MBSR) classes with men and may experience difficulties during certain aspects of the course (e.g., closing eyes during meditation practice), particularly in a mixed-gender setting. Several studies (two of men and women Veterans, and one of civilian women with a history of PTSD) found the group format to be an impediment to MBSR participation, citing interpersonal dynamics and discomfort with the mixed-gender class environment. Along with lack of time and schedule conflicts, "aversion to groups" was the most-common "deal breaker" in a study of Veterans' experience with MBSR. Groups were cited as a major reason preventing women Veterans from enrolling in MBIs, affecting Veterans' ability to engage in the program, and fueling drop out, with some stating that they would have preferred an all-women group.48,70

**Taken together, these system-level and patient-level barriers** have negative implications for key indicators of sustainability: reach (the percentage of the population who actually receive the intervention), treatment effectiveness, and ultimately intervention impact (the product of effectiveness and reach in a target population). Without overcoming the above barriers, such interventions will fail to ultimately be successfully disseminated, implemented and used to help the many Veterans who are struggling with chronic pain.

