**Risk vs. Potential Benefit.** The proposed research poses "minimal risk" to subjects. There are no experimental procedures involved in this study. The potential risks to study participants include loss of privacy and confidentiality. There are no economic and minimal social risks of participating in the study. The surveys will not ask very sensitive questions and subjects can refuse to answer any question(s). The potential risks associated with the individual interviews include psychosocial stress (any research project with direct contact with human subjects contains some risk of deleterious effects due to psychosocial stress). This is true for both usual care as well as intervention groups.

Mindfulness-based interventions are regarded as relatively safe interventions. A 2018 systematic review examining the safety of randomized controlled trials of mindfulness-based interventions found very few adverse events, with no significant differences in reported adverse events between intervention and control groups. Nonetheless, we have developed a crisis management protocol to address issues involving participant safety and systematically collect safety information, including severe adverse events (SAEs), unanticipated problems (UAPs), and adverse events (AEs). In the follow up questionnaires, participants will be asked to report side effects/adverse events related to the interventions by choosing from a list generated from the literature and the investigators' experience (see below).

Since you started your participation in the study have you experienced any of the following. Check all that apply.

- 1. Increase in disturbing memories
- 2. Feeling more upset than usual when something reminded you of the past
- 3. Increased feelings of sadness
- 4. Increased feelings of anxiousness

5. Seizures

- 6. Feeling more tired or fatigued than usual
- 7. Feeling more isolated or lonely

8. Other physical or mental symptoms; please specify: \_\_\_\_\_\_

If yes, please explain further:

Specifying conditions that would trigger an immediate suspension of the research is not applicable to this minimal risk study. If information does arise that necessitates communication, the study team will contact participants by phone and providers via encrypted email.

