We are seeking a waiver of documentation of informed consent for the PCT portion of the study, the "pre-implementation" follow-up surveys with a portion of intervention participants, and recontacting a portion of the pre-implementation follow-up survey completers. We are not asking sensitive questions in this survey. Asking subjects to return signed consent and authorization documents for this minimal risk study would dramatically reduce response rates and introduce bias. Additionally, the signed consent form would potentially increase risk for loss of privacy as all identifying information will be destroyed as soon as feasibly possible. Participants will receive mailed, pre-notification (postcard or letter, depending upon the recruitment approach; see Section 5.2) that contains an opt-out option for those who do not want to be contacted any further. Participants in recruitment approach #1 (postal mail only) will receive, with their prenotification letter, an information sheet containing: 1) information explaining the risks and benefits of study participation, 2) their rights as study participants and their privacy rights and 3) required elements of informed consent. Participants in recruitment approach #2 (postal mail + email) will be given a link to an electronic copy of the information sheet, as part of their email recruitment packet. Randomized participants in recruitment approach #2 will be sent a paper copy of the information sheet in their randomization packet.

Prior to randomization, participants will be contacted via a phone call in which all participation components will again be reviewed. This will include requiring participants to provide an emergency contact person and explaining that study staff will do the following if they are concerned about a participant's or others' safety. Study staff will explain: If we are concerned for your immediate safety, we may try calling, and/or emailing you, contacting your emergency contact person, and will then escalate further (for example, asking the Veteran Crisis Line staff to contact you, asking the Suicide Prevention team at your VA site to contact you, or asking your local police to do a wellness check) as it seems necessary to protect you or others. Only if participants agree to continue, they will be randomized a study group.

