#### Measures

#### Table 2: Study Measures

			6	12
Legend: EHR: Electronic Health Record; S: Survey; M: Mobile		10	m	m
app; F: Facilitator Records	BL	wk	0	0
Flow data (recruitment, enrollment, intervention adherence and				
fidelity, data collection rates)	х	Х	Х	х
Demographic and health-related characteristics				
Demographics, physical & mental health characteristics, military				
sexual trauma screen, medication use, prior treatment for pain,				
pain over past 6 months (S, EHR)	х			
EFFECTIVENESS MEASURES				
Primary Outcome				
Pain Intensity and Interference (Brief Pain Inventory Total Score;				
BPI) (S)	х	х	х	х
Secondary Outcomes				
Physical function, anxiety, depression, fatigue, sleep disturbance,				
participation in social roles and activities, patient-ratings of				
improvement, PTSD (S)	х	Х	х	Х
Process Measures				
Medication, health care utilization related to pain treatment (S,				
EHR)	х	х	х	х
Satisfaction (S)		х		
Adverse events (S; Veteran report; events reported to C-IRB)		Х	Х	Х
Pain management self-efficacy Pain Self-Efficacy Questionnaire'				
PSEQ) (S)	х	х	х	х
Pain catastrophizing, Pain Catastrophizing Scale (PCS) (S)	х	Х	Х	Х
Applied Mindfulness Process Scale (AMPS) (S)	х	Х	Х	Х
Perceived stress (NIH Toolbox Perceived Stress Fixed Form) (S)	х	х	Х	Х

LAMP Version 16, March 25, 2024 VA Central IRB Protocol Template - version 10/26/2012 Page 41 of 60

Amount of meditation practice, app use, and class attendance (M,				
F, S)		Х	х	х
Use of non-pharmacological pain management strategies (S)	Х	Х	х	Х
COVID-19 questions	х			

**Baseline Measures** will include demographic data (assessed by self-report and the EHR) and clinical data (assessed by the EHR) to capture common mental health comorbidities (e.g., depressive disorder, PTSD, anxiety, sleep-related disorders, and substance use disorders), medication use, and prior treatment for pain. These will be assessed by the baseline survey. We will also include the Pain Management Collaboratory Coronavirus Pandemic (COVID-19) Measures, comprised of seven items assessing the potential impacts of the coronavirus pandemic.

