**Our Primary Outcome will be pain severity and functioning**, defined as a change in the Brief Pain Inventory (BPI) total score (assessed by survey). The Brief Pain Inventory (BPI) assesses two key domains—intensity and interference—recommended for pain studies and has been validated in primary care. The BPI is the average of pain intensity and pain interference scores. The pain intensity score is an average of 4 ratings of 0 (no pain) to 10 (pain as bad as you can imagine) for current, least, worst, and average pain in the past week. The pain interference score averages seven ratings, 0 (does not interfere) to 10 (interferes completely), of interference with general activity, mood, walking ability, normal work, relations with other people, sleep, and enjoyment of life. The BPI has been shown to be highly responsive to change in clinical trials and to have strong internal consistency (Cronbach's  $\alpha = 0.77$ ).

**Secondary Outcomes.** To facilitate data sharing and comparison between studies we have incorporated Common Data Elements (CDEs), for use in our patient surveys. Specifically, we will use measures from the PROMIS-29 Profile v2.0 Instrument (www.nihpromis.org) as recommended by the NIH Research Task Force. This includes quality of life, emotional functioning and mental health-related outcomes (anxiety, depression), and outcomes related to fatigue and sleep. Self-reported data will also be collected on PTSD symptoms using the PTSD checklist (PCL), version C, DSM-V update, and patient satisfaction (using a short measure used by investigators [name] and [name]). These outcomes will be assessed via survey.

Adverse events will be monitored throughout the study period, using a process similar to other MBIs with Veterans. Specifically, Veterans will be given contact information encouraged to report exacerbation of symptoms or adverse effects to the class facilitators or study coordinator.

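### The risk and consent text denies sensitive survey questions, yet a self-reported PTSD checklist is in all four surveys and no crisis contact is stated to reach a respondent online

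*Combined protocol and SAP*

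**What the plan says.** Five places bear on this point.

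- **Section 5.1, Risk vs. Potential Benefit (Aim 1).** The survey risk is described as: "The surveys will not ask very sensitive questions and subjects can refuse to answer any question(s"). The paragraph names loss of privacy and confidentiality as the main risks and attaches psychosocial stress to the individual interviews. It also mentions a crisis management protocol.
- **Section 5.3a, consent procedures for Veterans.** In the request to waive documentation of consent, the text says: "We are not asking sensitive questions in this survey". The request covers the trial, the pre-implementation surveys and later re-contact.
- **Section 5.5a, Table 2.** PTSD closes the secondary-outcome row, "improvement, PTSD (S"), which is marked at baseline and at all three follow-ups. The baseline characteristics row includes a military "sexual trauma screen, medication use, prior treatment for pain" and ends "pain over past 6 months (S, EHR").
- **Section 5.5a, text on measures.** The PTSD instrument is confirmed: "Self-reported data will also be collected on PTSD symptoms using the PTSD checklist (PCL), version C, DSM-V update". The baseline paragraph takes clinical data from the EHR, then adds "These will be assessed by the baseline survey". It does not mention the trauma screen.
- **Section 5.1, safety text after the adverse-event list.** Crisis contacts go into printed study materials and the mobile app. The staff procedure for distress applies when it arises in a group session or during a phone call.

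**The concern.** A body that waives documentation of consent relies on the protocol's account of what participants will be asked. A statement that nothing very sensitive is asked, or nothing sensitive at all, sits badly beside a trauma-symptom checklist given at every assessment. If the trauma screen is also asked by survey, the gap widens: Section 2.0 defines that trauma to include "physical assault of a sexual nature, battery of a sexual nature, or sexual harassment".

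The practical stake is participant safety. Because survey distress is not listed as a risk, no safeguard is described at the point where it could arise. A person who becomes distressed while answering the online baseline survey is not in a group or on the phone, and does not yet have the app.

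**Working it through.** The plan gives no figure to reproduce. The check sets the statements side by side and counts from Table 2.

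**1. Is a sensitive instrument in the surveys?** For the PTSD checklist the answer is clear. Its only source code is survey, and its row is marked at 4 of 4 time points (baseline, 10 weeks, 6 months, 12 months). The adverse-event list printed in Section 5.1 for the follow-up questionnaires also asks about disturbing memories and about being upset by reminders of the past.

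**2. Is the trauma screen asked by survey?** The documents do not settle this. It appears at 1 of 4 time points (baseline). The source code covers a mixed row of demographics, health characteristics, medication and prior treatment, and is not assigned item by item. The baseline paragraph points to both sources and omits the screen.

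**3. Does the Section 5.3a sentence cover the trial surveys?** Possibly. The preceding sentence starts with the trial and ends with those who complete the pre-implementation survey, so the singular reference could be to either. Section 5.1 refers to surveys in the plural and has no such ambiguity.

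**4. Do the stated safeguards reach the online respondent?** The order of events is as follows.

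| Step | Source | Crisis contact or distress procedure stated? |
|---|---|---|
| Recruitment letter, or postcard and email | 5.2 | Not stated; printed materials may carry contacts |
| Screener, then chart review | 5.2, 5.4a | Chart review excludes suicidality, severe depression, active psychotic symptoms and mania |
| Baseline survey, with PTSD checklist | 5.4a, Table 2 | Not stated for the survey itself |
| Call before randomisation, explaining safety escalation | 5.3a | Yes |
| Randomisation; app and welcome packet for the two intervention arms | 5.1 | Yes, through the app and printed materials |
| Follow-up surveys, all arms | Table 2 | Not stated for the survey itself |

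Under the email approach, Section 5.3a sends the paper information sheet only after randomisation. Before the baseline survey, the one printed item described for these recruits is a postcard. Usual-care participants are not described as receiving the app at any stage.

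**5. How many people does this touch?** Section 5.6 plans at least 250 per arm, so 250 × 3 = 750, with a ceiling of 950. Section 5.4a requires a completed baseline survey before randomisation, so all 750 to 950 meet the checklist at least once. With full follow-up that is 750 × 4 = 3,000 to 950 × 4 = 3,800 administrations at most.

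**The case against.** The strongest reply is that the phrase in Section 5.1 is a judgement of degree. The same sentence lets anyone refuse any question. Chart review removes those thought most vulnerable, surveys can be completed on paper or by phone, and the protocol that carries the sentence also carries Table 2, so the measures were disclosed to the IRB. All of this stands. It limits the point to inconsistent wording and a gap in where contacts appear.

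Several stronger readings are tempting, but the documents do not support them.

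- **That the minimal-risk class is wrong.** Nothing in the documents shows this.
- **That participants are misinformed.** They receive an information sheet on risks and benefits whose text is not available here.
- **That 45 to 190 women would be asked about their own trauma.** The arithmetic is 750 × 0.40 × 0.15 = 45 and 950 × 0.50 × 0.40 = 190, using the 15-40% prevalence in Section 2.0 and 40-50% women. It holds only if the screen is asked by survey and if a prevalence for women using VA services applies to this sample.
- **That trauma items would cause abandoned baseline surveys and block randomisation.** No abandonment is reported, and nothing says that a refused item makes the survey incomplete.

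**Conclusion.** The point holds in a limited form. The Section 5.1 statement conflicts with Section 5.5a and Table 2, on the ordinary view that a PTSD symptom checklist is sensitive. The Section 5.3a statement conflicts too if it covers the trial surveys; otherwise it needs only a clearer reference. The source of the trauma screen is undefined. Survey distress is missing from the listed risks, and the safeguards described are not stated to reach a person answering online, before randomisation or later.

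The checklist affects every randomised participant, at 4 of 4 surveys. Sample size, power and the primary BPI analysis are unaffected. The case for acting is that the description should be accurate for a waiver decision, and that the safety gain is cheap.

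**What to change.** 1. In Section 5.1, say that the surveys include PTSD symptom questions and may cause distress, and list that distress among the risks. Amend Section 5.3a in the same way and make clear which survey its sentence refers to.
2. In Table 2 and the baseline paragraph, state whether the military sexual trauma screen comes from the survey, the EHR or both.
3. Show the crisis contacts already prepared under Section 5.1 beside the PTSD items in the online and paper surveys, and beside the trauma item if it is asked.

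The cost is a wording amendment and one screen of existing text. Removing the trauma screen from the survey is not needed for consistency. It would be a trade-off, because the EHR entry may be missing for some participants.
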